1.4 Study Design

The trial is a 12-week, single-arm, eucaloric, controlled-feeding trial. During weeks 1–4 (Ramp-Up Phase), adults with insulin-independent T2D progressively eat more fruit, starting at 10% of daily energy and incrementally increasing to 50% while remaining weight-stable. During weeks 5–12 (Main Phase), participants eat 50% of their energy requirements as whole fruit (~16.4 servings/day) and the remaining 50% as a Mediterranean-style diet. By design, the aggregate diet is a high-carbohydrate diet, rich in simple carbohydrates in whole-food form. Food is prepared for participants in a metabolic kitchen, and participants must eat the provided study food. At week 10, participants who achieve non-diabetic levels of glycemia—defined as mean 24-hour glucose <140 mg/dl (equivalent to HbA1c <6.5% or <)—are taken off their antihyperglycemic medications to see if they can maintain non-diabetic glycemia without the use of medication. All study outcomes are measured at week 0 (baseline), week 4 (end of Ramp-Up Phase), and week 12 (end of Main Phase).

1.5 Participants

We will enroll 16 adults recently diagnosed with insulin-independent T2D. We modeled our eligibility criteria on the landmark DiRECT study, which found that a VLCD intervention induces T2D remission in 46% of patients [3]. Like the DiRECT study, we are recruiting adults with insulin-independent T2D who were diagnosed with T2D within the past six years, as patients with diabetes durations longer than 6–8 years are less likely to achieve remission.² Table S1 in the appendix shows the eligibility criteria. To be eligible, applicants must have an HbA1c between 6.0–9.5%, be aged 20–70 years, and have a body mass index (BMI) \leq 45.0 kg/m². Key exclusion criteria include an estimated glomerular filtration rate (eGFR) <45 ml/min per 1.732 m², a change in body weight >5 kg in the past six months, a change in a chronic medication dosage that may affect study endpoints within the past three months, a significant health condition that might compromise the participant's safety or data validity, or inability to follow the study protocol. All participants must provide written informed consent prior to enrolling in the study. Participants are provided with a stipend, food, and a high-speed blender as compensation.

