2.7 Compliance

To ensure compliance during the controlled-feeding intervention, participants record themselves while preparing smoothies and eating all provided study food. We are using a previously validated method called remote video monitoring.⁴ In brief, we provide participants with an encrypted smartphone and tripod and teach them how to record themselves. Participants record themselves while eating all the provided food and preparing the smoothies. Research staff review the recorded videos for compliance and estimate the portion sizes of any uneaten food. We quantify compliance in based on the percent of the provided food calories consumed. Compliance rates below 80% or dishonesty are grounds for withdrawal.

3. Assessments

We will perform all assessments as detailed below.

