4.3 Power Calculation

As this is a pilot and feasibility trial, the sample size was not based on a power calculation. We selected a sample size of 16 completers to provide sufficient data to inform the design of a future trial. Nonetheless, our study has 81% power to detect an 18.0% rate of attaining non-diabetic glycemia vs. a spontaneous remission rate of 0.7%.²³ Further, 16 completers provides 80% power to detect effect sizes of Cohen's d ≥ 0.78 , using a two-tailed paired t-test with α =0.05. This corresponds to a large effect size, which we expect, as participants eat a very large amount of fruit. We acknowledge that we are not powered to detect medium or small effect sizes, which may also be clinically relevant.

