4.4 Statistical Analyses

All statistical tests will be two-sided with a Type I error rate of α =0.05. Because this is a controlled-feeding trial—designed to determine the cardiometabolic effects under conditions of nearly perfect adherence—we will analyze the data per protocol in completers only. The primary comparison will be between weeks 0 and 12, with secondary comparisons between weeks 0 and 4 and between weeks 4 and 12. Data may be Winsorized if there are outliers with an overwhelming degree of influence or values that are non-physiologic . We will test whether a fruit-rich diet can induce non-diabetic glycemia without hyperglycemia medications by testing whether our observed "remission" rate differs from the spontaneous T2D remission rate of

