0.07% using an exact binomial test.²³ If there is one or more cases of non-diabetic glycemia, then the true rate is non-zero, and we will report a 95% confidence interval derived from bootstrapping. All other data will be analyzed as change scores. For all continuous data and Likert score data with at least four levels and sufficient variability, we will use linear mixed models with time as either a linear or categorical effect and with a random intercept for participants. For other data types, we will use distribution-appropriate generalized linear mixed models. Alternatively, if spline models are more parsimonious than treating time as a linear or categorical effect, we will use generalized-additive models with penalized adaptive regression splines instead. To analyze the data from CGM, we will perform a trajectory analysis to determine whether there are different "response phenotypes." Since it is conceivable that participants starting from very different baseline diets may have distinct trajectories early on, we may also consider a trajectory analysis of the data with special attention to the Ramp-Up phase and restrict the models to the Main Phase period after the trajectories converge. We will consider adjusting for covariates such as baseline values or mean 24-hour glucose levels only if statistically and clinically merited. For the inferential statistics on continuous variables, we will test for differences using least squares means evaluated at study timepoints, or alternatively, if time is most appropriately treated as a categorical variable, by the significance of the coefficient for each timepoint. We will analyze change in categorical variables using McNemar's test for dichotomous variables and Bowker's test of symmetry for variables with more categories. Finally, to assess inter-individual responses in the vein of precision nutrition, we will also report the percentages of participants who experience an improvement, no change, and a worsening in glycemic control.

5. Protocol Amendments

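### Section 1.5 enrols 16 participants while Section 4.3 bases its power on 16 completers; with a completers-only analysis, the two agree only if nobody withdraws

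*Combined protocol and SAP*

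**What the plan says.** Section 1.5 of the combined protocol and SAP gives the size of the trial as a number enrolled: "We will enroll 16 adults recently diagnosed with insulin-independent T2D". Section 4.3 gives it as a number completing: "We selected a sample size of 16 completers to provide sufficient data to inform the design of a future trial".

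Section 4.3 also says that "the sample size was not based on a power calculation", because this is a pilot and feasibility trial. It then reports two power figures. For the binary outcome it claims "81% power to detect an 18.0% rate of attaining non-diabetic glycemia vs. a spontaneous remission rate of 0.7" per cent. For continuous outcomes it claims that 16 completers give 80% power for a Cohen's d of 0.78 or more, by a two-tailed paired t-test at the 0.05 level.

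Section 4.4 sets the analysis population: "we will analyze the data per protocol in completers only". It also describes the test of the binary outcome, where the reference rate reads "0.07% using an exact binomial test". Section 2.7 gives reasons for removing participants: "Compliance rates below 80% or dishonesty are grounds for withdrawal". No section gives an expected dropout rate, a replacement rule or a maximum number of starters.

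**The concern.** The same number, 16, is attached to two different counts. Because only completers are analysed, each unreplaced withdrawal takes one person out of the analysed sample. Losses are plausible: for 12 weeks participants eat provided food and record themselves eating it, with fruit reaching half of daily energy, and the protocol itself makes low compliance grounds for withdrawal.

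One of the two statements therefore has to give way once anyone leaves. If Section 1.5 governs and nobody is replaced, fewer than 16 people are analysed and the power in Section 4.3 describes a sample that the trial will not have. If Section 4.3 governs, more than 16 must be enrolled, Section 1.5 is wrong, and the number who start is left open. In a pilot meant to inform a later trial, the ratio of starters to completers is itself a result that the next team will need.

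**Working it through.** **Inputs.** From Section 4.3: 16 completers, alternative rate 18.0%, null rate 0.7%, d = 0.78, two-sided alpha 0.05. From Section 4.4: exact binomial test, completers only. From Section 1.5: 16 enrolled. The documents give no dropout rate, so losses of 0 to 4 are an assumption, shown as a range.

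**Reproducing the 81%.** With n = 16 and a null rate of 0.007, the chance of at least one responder is 1 − 0.993^16 = 0.106, so one responder is not significant. The chance of at least two is 1 − 0.993^16 − 16 × 0.007 × 0.993^15 = 0.0055, so the test rejects at two or more. At a true rate of 0.18:

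Power = 1 − 0.82^16 − 16 × 0.18 × 0.82^15 = 1 − 0.0418 − 0.1468 = 0.8115.

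The stated 81% is reproduced. The cut-off of two responders is the same for every n from 12 to 16.

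**With one and two fewer completers.**

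- n = 15: 1 − 0.82^15 − 15 × 0.18 × 0.82^14 = 1 − 0.0510 − 0.1678 = 0.7813.
- n = 14: 1 − 0.82^14 − 14 × 0.18 × 0.82^13 = 1 − 0.0621 − 0.1910 = 0.7469.

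**The paired t figure.** Power comes from the noncentral t distribution with n − 1 degrees of freedom and noncentrality d × √n. At n = 16 the noncentrality is 0.78 × 4 = 3.12 and power is 83.0%, not 80%; the d that gives 80% is 0.75. The stated pair (80%, 0.78) matches n = 15, where power is 80.2%. This figure therefore has one participant of slack.

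| Completers | Unreplaced withdrawals from 16 | Power, 18% vs 0.7% | Power at d = 0.78 | d with 80% power |
|---|---|---|---|---|
| 16 | 0 | 81.2% | 83.0% | 0.75 |
| 15 | 1 | 78.1% | 80.2% | 0.78 |
| 14 | 2 | 74.7% | 77.0% | 0.81 |
| 13 | 3 | 70.8% | 73.3% | 0.85 |
| 12 | 4 | 66.4% | 69.2% | 0.89 |

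**Dependence on the null rate.** If 0.07% were the operative null, the chance of at least one responder among 16 would be 1 − 0.9993^16 = 0.011. One responder would then be significant, and power would be 1 − 0.82^n: 95.8% at n = 16, 94.9% at n = 15 and still 86.3% at n = 10. The binomial column above applies only under 0.7%.

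**Starters needed for 16 completers.** Using 16/(1 − dropout), rounded up, with assumed dropout: 17 at 5%, 18 at 10%, 19 at 15%, 20 at 20% and 22 at 25%.

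**Why the number started matters.** As an illustration with assumed counts, 3 responders among 16 completers is 18.8%; if 20 people had started, it is 15.0% of starters.

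**The case against.** The strongest reply is that Section 4.3 is the section that sets the sample size, and it does so in completers. Section 1.5 is a general description of participants and may simply be loosely worded. If recruitment continues until 16 people complete, both power statements stand and the error is one phrase. Nothing in the documents excludes this. A reader might infer that the stated power is out of reach; the documents do not support that, because no section says that enrolment stops at 16 or that withdrawals will not be replaced.

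A reader might also infer that any single withdrawal defeats both power figures. It does not: the 80% at d = 0.78 survives one withdrawal and is lost only from two.

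Three further points limit the consequence. First, the protocol says outright that the size did not come from a power calculation, so no decision about the size rests on 81% or 80%. Second, the null-rate conflict between Sections 4.3 and 4.4 moves the binomial power more than a few withdrawals would. Third, the Barriers Interview in Section 1.7 screens for obstacles to participation and should reduce dropout, though it cannot guarantee none.

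All of this stands, and it limits the size of the point. It does not remove the mismatch. The plan publishes two counts that agree only under zero attrition, and it does not say which one governs.

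**Conclusion.** The mismatch is real: 16 enrolled and 16 completers cannot both hold once anyone withdraws, and the plan does not say how losses are handled. Its effect on the stated power is conditional. If enrolment stops at 16 without replacement, one withdrawal costs about 3 points on the binary outcome (81.2% to 78.1%) and leaves the continuous figure at its stated level. Two withdrawals take both below their stated values. If recruitment runs until 16 complete, the power figures are unaffected by attrition, and what is missing is a corrected Section 1.5 and a commitment to report the number started.

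The binomial figures rest on the 0.7% null, and the number of withdrawals is assumed. The documents do not support a claim that the trial is too small for its purpose: it is a pilot, and its size was not derived from power. This should be corrected before the plan is relied on, but it does not put the design in question.

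**What to change.** Make Sections 1.5 and 4.3 agree, in one of two ways.

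1. If 16 completers is the target, change Section 1.5 to say that participants will be enrolled until 16 complete week 12, state that withdrawn participants are replaced, and commit to reporting the number who started alongside the completers-only results.
2. If enrolment is capped at 16, restate Section 4.3 for fewer completers, give the dropout assumption, and show a range. For 15, 14, 13 and 12 completers, power for 18% against 0.7% is 78%, 75%, 71% and 66%, and the d detectable with 80% power is 0.78, 0.81, 0.85 and 0.89.

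In either case, reconcile the 0.7% in Section 4.3 with the 0.07% in Section 4.4 before quoting any binomial power. If the text stays at 16 completers, note that 80% power there corresponds to d = 0.75.

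The cost is mainly wording. The first option may mean feeding and testing a few more starters (17 to 22 at the assumed 5% to 25% dropout). The second makes the stated power slightly less favourable.

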1.6 Setting and Recruitment

The clinical trial is being conducted at the University of Alabama at Birmingham (UAB). The trial was approved (IRB-300001719) by the UAB Institutional Review Board and is registered on ClinicalTrials.gov (NCT03758742). This study is being conducted in accordance with the Declaration of Helsinki.

We are recruiting a convenience sample of participants from the greater Birmingham, Alabama metropolitan area. We recruit participants through flyers placed around the university's campus, ads on the university's clinical trials website, earned media spots on local TV and radio shows, and by presenting the study to patients enrolled in diabetes education classes at UAB Hospital. We are also engaging Bump Digital Marketing

(https://recruitment.bumpdigitalmarketing.com/) to run ads on social media platforms, particularly Facebook and Google.

1.7 Screening

Interested individuals are prescreened via an online questionnaire and/or by phone, and those who pass prescreening are invited to screen in person. At the first screening visit, applicants sign the consent form, are screened against the eligibility criteria, and have their blood drawn to run a metabolic panel and measure HbA1c. After the first screening visit, the study physician reviews each applicant's laboratory results and medical history. Applicants deemed medically eligible then complete a three-day food record before returning for a second screening visit. During the second screening visit, we conduct a 30-45 minute semi-structured interview called a Barriers Interview. During the Barriers Interview, we ensure that each participant understands the demands of the study, and we assess any psychological, behavioral, and logistical barriers that may impede study participation. Only applicants capable of meeting all study demands are enrolled.

1.8 Schedule of Assessments

Table S2 in the appendix shows the schedule of assessments. We measure all outcomes at week 0 (baseline), week 4 (end of the Ramp-Up Phase), and week 12 (end of the Main Phase). Most outcomes are assessed during a 4–5-hour testing visit, with the exception that CGM, stool collection (for exploratory analyses), and the abdominal MRI/S scans are conducted during the

week prior. Before each visit, participants fast for at least 10 hours. During each testing visit, we start by measuring anthropometrics, heart rate, and blood pressure. Thereafter, we collect a fasting blood draw and administer a three-hour OGTT. During the last hour of the OGTT, participants complete a series of questionnaires on food cravings, eating behaviors, mood, quality of life, and depression. Once the OGTT is complete, participants complete a Sweetness Taste Test. At week 12, we also conduct an exit interview.

1.9 Participant Safety

Participants wear a CGM throughout the 12-week controlled-feeding intervention, which allows us to remotely monitor their safety. The study team reviews the CGM data at least twice per week. Values below 70 mg/dl or above 300 mg/dl are grounds for considering medication changes; though, we will attempt not to adjust antihyperglycemic medications until week 10 whenever possible. The study physician ([name]) makes all decisions on whether to adjust medications. In addition, we assess other the safety endpoints of blood pressure, heart rate, and adverse events once a week in our clinic. Every other week, we also draw blood to measure fasting lipids.

2. Dietary Intervention

2.1 Overview

The 12-week controlled-feeding intervention has two phases: (1) a four-week Ramp-Up Phase, during which participants progressively eat more whole fruit, and (2) an eight-week Main Phase, during which participants eat 50% of their energy requirements as whole fruit and the remaining 50% as a Mediterranean-style diet. During both phases, participants approximately maintain their weight and consume large amounts of whole fruit in three forms:

- frozen fruit smoothies (i.e., frozen whole fruit in blended form);
- fresh fruit in fruit salads; and
- dried fruit.

All study food is prepared in a metabolic kitchen. Participants are instructed to eat all of the provided food while being video-recorded to ensure compliance. Participants are also instructed not to change their current physical activity levels, sleep habits, medication use, and other health behaviors during the study.

2.2 Ramp-Up Phase: Weeks 1–4

We give participants a four-week ramp-up period to acclimate to the high fiber and low energy density of the diet. The ramp-up period allows participants to adapt to eating low-energy-density food and overcome any transient gastrointestinal or bowel symptoms. The ramp-up period also provides preliminary data on the effects of whole fruit alone on cardiometabolic health before the remainder of participants' diet becomes a Mediterranean diet. During the ramp-up period, participants gradually eat more whole fruit as follows:

- Days 1-2: 10% of calories in the form of a frozen fruit smoothie;
- Days 3-7: 20% of calories in the form of a frozen fruit smoothie;
- Week 2: 30% of calories, with 25% as a smoothie and 5% as dried fruit;
- Week 3: 40% of calories, with 25% as a smoothie, 10% as dried fruit, and 5% as a fresh-fruit salad;

• Week 4: 50% of calories, with 25% as a smoothie, 12.5% as dried fruit, and 12.5% as a fresh-fruit salad.

To remain weight stable, participants are instructed to reduce their habitual diet in proportion to the amount of fruit added.

2.3 Main Phase: Weeks 5–12

During weeks 5–12, participants consume a whole-fruit-rich diet that provides 50% of calories as whole fruit. The purpose of the main phase is to determine the effects of a whole fruit-rich diet while matching all aspects of the diet across participants, while also simultaneously maximizing the possibility that participants may be able wean off all their anti-hyperglycemic medications. The fruit composition of the diet is:

- Frozen fruit smoothie: 25% of calories;
- Fresh fruit salad: 12.5% of calories;
- Dried fruit: 12.5% of calories.

We deliberately include dried fruit and other fruits that do *not* have a low glycemic index, instead of only focusing on low-glycemic index fruits, to test fruits that are more representative of what people eat. Although most dried fruit has a moderate glycemic index, it does have a low glycemic load. During the Main Phase, the fruit smoothies also contain a small amount of other foods, such as a cup or two of leafy greens (green smoothies) and/or a couple tablespoons of flax or chia seeds. The remaining 50% of daily calories comes from Mediterranean-style diet. Participants must consume all the provided study food and only consume the provided food during the 12-week controlled-feeding intervention, except for two break meals per week. For the break meals, participants may substitute any meal of their choice for a non-fruit-containing study meal. Participants are permitted to drink zero-calorie beverages and add zero-calorie spices without salt to meals. Participants can eat study meals in any order as long as they consume either (a) the smoothie or (b) both the fresh salad and dried fruit by noon. We implemented this rule to help participants overcome the challenge of eating a low-energy-density diet by requiring participants to spread out their fruit consumption across the day. Additionally, participants must eat meals in one sitting, except for the fruit smoothies and fresh-fruit salads, which they can eat in two sittings. Finally, participants check off each study food item they eat or do not eat on a provided checklist. We also instruct participants to record any non-study food or beverage they consume on the food checklist.

2.4 Menu Design

For the Main Phase of the trial, we designed a seven-day rotating menu that provides 50% of calories as whole fruit and the remaining 50% of calories as a Mediterranean-style diet (Figure S1 in the appendix). We define a Mediterranean diet as a plant-centered dietary pattern that emphasizes vegetables, whole grains, legumes, nuts/seeds, olive oil, and seafood and minimizes dairy, poultry, eggs, highly refined foods, and red meat. In our menus, we intentionally incorporated small amounts of dairy, bread, and poultry and omitted red meat and processed meat.

The aggregate diet is a high-carbohydrate diet, providing 62% carbohydrate, 26% fat, and 12% protein. The diet is rich in simple carbohydrates and fructose while also being very high in fiber and low in energy density (3.85 kilojoule/g [0.92 kcal/g]). A 10,460 kilojoule (2,500 kcal) diet provides 16.4 servings of fruit, 81 grams of fiber, 243 grams of total sugars, 77 g of fructose, 11 g of saturated fat, and 1,871 mg of sodium. It also provides 6.4 servings of vegetables, 2.6

servings of nuts and seeds, 1.5 servings of legumes, 1.0 servings of whole grains, 0.9 servings of meat, and 0.8 servings of dairy per day. In total, there are 22.8 servings of fruits and vegetables. We designed the menu to meet the estimated average requirements (EARs)—or adequate intakes (AIs) when there is no estimated average requirement—for the mean person aged 31–50 years for all nutrients except Vitamin D. Because it took tweaking to formulate a menu with adequate zinc for males, we do not recommend eating >50% fruit in conjunction with a low-animal product Mediterranean diet without very careful planning or adding more zinc-rich foods.

